5.0 Study Procedures

Screening Visit

This will occur in the Vanderbilt Clinical Research Center (CRC). Subjects will arrive in a fasting (at least 6 hours with no food or drink) state. After informed consent has been obtained, inclusion/exclusion criteria will be reviewed to confirm that the subject meets study eligibility requirements. Subject's medical history and concomitant medications will be discussed and documented. Subjects will then undergo a physical exam, including measurement of height and weight, and "vital signs" (blood pressure and heart rate). Subjects will have a 5ml (1/3 tbsp) fasting blood draw in order to assess glucose, electrolyte and fluid balance, and kidney function, and will undergo a urine pregnancy test (if the woman is of child-bearing potential). Subjects will speak with study personnel who will review physical activity level and any food restrictions or allergies. You will be asked questions about your ability to undergo an MRI scan, including questions about metal implants. Study personnel will review the low- and high-salt dietary protocols and provide the subject with study diet instructions. If needed, study personnel may then schedule an appointment for the subject to meet with a dietitian for further review of dietary needs. If subject agrees to adhere to study diets, then randomization (using permuted blocks) will occur to one of two aforementioned dietary sequences: (1) high-salt, washout, then low-salt diet, or (2) low-salt, washout, then high-salt diet.

The subject will then be given instructions on 24-hour urine collections, which will be obtained at 4 study time points (baseline, end of diet 1, end of washout, and end of diet 2). A baseline study visit will then be scheduled. Additionally, all subjects will be asked to discontinue use of the following over-the-counter-medications (NSAIDS, decongestants, cold medicines) one week prior to study and to remain off these agents until the study is completed.

Baseline Visit

In the 24-hours prior to the baseline visit, the subject will collect urine for quantification of urine sodium excretion and creatinine. For the baseline visit, the subject will arrive to the CRC in a fasting (at least 6 hours with no food or drink) state, return the 24-hour urine collection, and then be asked to lay supine. A physician or study research coordinator will review the subject's medical history to assess for any changes since screening that may potentially exclude the subject from participating. After 1 hour and while the subject is still supine, the CRC nurse will record blood pressure and heart rate (average of 3 measures made 5 minutes apart) in the left arm using an automated cuff. The CRC nurse will also draw venous blood samples (25 ml = 1 3/4 tablespoons) for measurements of a basic metabolic panel and plasma renin. Blood samples (cells, plasma and serum) may also be collected for storage at -80°C for future investigations. The subject will be given another 24-hour urine collection kit, and diet 1 materials. If the subject was randomized to begin with the low-salt diet, he or she will pick up the prepared low-salt meals from the CRC. If the subject was randomized to begin with the high-salt diet, he or she will receive high-sodium bullion packets.

MRI Exam

The subject may undergo a baseline MRI scan on the same day as the baseline visit or on a separate day, to occur either before beginning study diets, or at least 1 week after the diet 2 visit. The subject will undergo the following noninvasive magnetic resonance imaging (MRI) scan at the Vanderbilt University Institute of Imaging Science (VUIIS), following an established protocol (no longer than 1.5 hours total) to quantify baseline tissue sodium content, whole-body fat composition, lymphatic function, and kidney vascular function. No MRI methods used require the administration of any exogenous contrast agents, and therefore will be completely non-invasive. In total, noninvasive MRI protocols will be applied within a 90-minute scan session.

Tissue sodium content can be visualized and quantified non-invasively in humans with MRI.²⁷⁻³¹ Sodium content in leg will be imaged with a detector tuned to sodium resonance (Rapid, Germany) and a 3.0T MRI scanner (Ingenia Elition, Philips Medical Systems, Best, The Netherlands). Four tubes containing aqueous solutions with 10, 20, 30, and 40 mmol/L NaCl will serve as calibration standards by relating intensity to a concentration in a linear trend analysis. In parallel, we will quantify tissue water content using conventional MRI methods, including a fat-saturated inversion recovery sequence with spin density contrast.²⁷⁻²⁹ The total acquisition time for this protocol is 15 minutes.

Body composition including fat/water fraction will be measured using a whole-body multi-echo Dixon MRI (AMRA® Body Composition Protocol³², AMRA Medical AB, Linkoping, Sweden). Volunteers will be positioned supine, head-first in the MRI scanner. The total acquisition time for this protocol is 6 minutes.

A 16-channel torso coil will be placed over the lower extremities of the volunteer. Noninvasive MR lymphangiography will be performed to measure lymphatic vascular function in the legs³³. The total acquisition time for this protocol is 11 minutes.

With the torso coil placed over the abdomen, the kidneys will be imaged with MR relaxometry^{34, 35} and an arterial-spin-labeling sequence applied bilaterally over the kidneys and renal artery to measure cortical perfusion. The total acquisition time required for kidney imaging is 10 minutes.

Biophysical Exam

During the baseline visit and at the time of MRI, body composition will also be measured using bed-side, biophysical instruments: a bioimpedance spectroscopy unit (L-Dex U400) and/or a tissue dielectric probe (MoistureMeterD) in the arms and legs, and locations of interest on the body. This will require approximately 15 minutes while resting supine, and results are intended to determine whether accessible, bed-side devices can provide similar information as MRI.

Low- and High -Salt Diets

All low-salt meals will be provided to participant by the study. Subjects will pick up the prepared meals, snacks, and sodium free water at the CRC at times and intervals most convenient to the participant. The low-salt diet will include a maximum of 600mg (26 mEq) of sodium per day. Subjects are encouraged to consume all food as provided and expected to have no substitutions or additions. The calorie needs for weight maintenance will be assessed at screening. The low salt meal plan contains 2500-2800 calories. This calorie level is sufficient for the majority of the research population. Additional low-salt snacks will be added as need should the subject require additional calories. The high-salt diet supplies will consist of the subject's "usual" diet, supplemented with 2 bouillon broth packets each day, which will be provided by the study personnel. Each broth packet contains 48 mEq sodium for a total of approximately 100 mEq additional sodium intake per day. This method conveniently raises total salt intake to >200mEq/day (> 4,600 mg sodium/day) in over 95% of healthy volunteers obviating the need for additional prepared meals and visits.

Subjects, while on the low- and high-salt phases of the diet, will receive calcium supplementation. Calcium will be supplied by 2 antacid tablets taken by mouth; each will provide 750 mg of calcium.

Diet 1 visit

The same protocol as the baseline visit (described above) will be followed, with the exception that the subject will not undergo MRI. Other study procedures, including return of the 24-hour urine collection, blood pressure, and heart rate measures, obtaining venous blood draw in the supine position will be identical to the baseline visit. The biophysical exam may be performed while subjects are laying supine. After this Diet 1 visit, the subject will enter a minimum seven-day washout period. This will consist of the subject adhering to their "usual" diet. They will be given their 24-hour urine collection kit, to be completed before the "washout" visit.

Washout visit

The same protocol as the baseline visit will be followed, except that subjects will not undergo MRI. After this washout visit, the subject will crossover to the opposite salt diet from week 1. They will also be given their 24-hour urine collection kit.

Diet 2 visit

Protocol Version: 5
Protocol Date: 07/27/2020

Subjects will undergo the same procedures as in the Diet 1 visit (see above), except a 24-hour urine collection kit will not be given.

Biomarkers

Blood and urine samples will be coded for subject confidentiality. Measurements of interest will be performed at Vanderbilt University. For possible future investigations, excess blood and urine samples may be frozen and stored in the Vanderbilt University Core lab for Cardiovascular Translational and Clinical Research.

6.0 Risks

Venous Blood draw: This is a routine procedure that is considered standard of care in clinical medicine. At each visit, subjects will undergo a single venous blood draw. All blood draws will be performed by trained personnel using universal precautions to protect both the subject and personnel. The risks to subjects are minimal, but may include pain, allergic reaction, infection or bleeding at the needle stick site. These usually resolve without any specific medical therapy over the course of minutes to days.

MRI: Magnetic Resonance Imaging is routinely performed in clinical medicine. All imaging scans performed in this study are non-invasive (i.e., they do not require any injection of exogenous contrast agents or ionizing radiation) and therefore risks to subjects are low. Power monitoring and gradient switching speeds at 3.0T are applied according to the general FDA guidelines for MRI and controlled by the scanner company software. The effects of magnetic fields in an MRI scanner have been extensively studied and there are no known significant risks with an MRI exam. Subjects may, however, be bothered by feelings of confinement or claustrophobia, and by the noise made by the magnet during the procedure. Subjects will be asked to wear earplugs or earphones while in the magnet. Subjects may not participate in this study if they have a pacemaker, an implanted defibrillator or certain other implanted electronic or metallic devices for which MRI is contraindicated. Questioning prior to enrollment will determine if subjects have had brain surgery for a cerebral aneurysm, or have implanted medical or metallic devices, shrapnel, or other metal, such as metal in the eye. If subjects move rapidly within or around a magnet with a field of 3.0T they may feel dizzy. We therefore advise them to move slowly and, once they are positioned on the table, we will move the person into the magnet slowly. Emergency personnel and equipment will be on hand during the MRI for safety. If at any time subjects feel excessive feelings of confinement or claustrophobia, the scan may be terminated by the subject. The total time on which the participant is in the MRI scanner is estimated to be no longer than 90 minutes.

Biophysical Exam: The external measurements taken during the visit are applied using standard procedures and are fast to administer using non-invasive tools that do not bring on any discomfort to subjects, are FDA-approved or determined safe for human use, and are taken within a couple of minutes while subjects are lying down. Subjects who have open

wounds at the site of measurement, are pregnant at the time of exam, or have an implanted device with a battery, such as a pacemaker, will not be allowed to receive the biophysical exam.

Tolerability and safety of salt diets: While there is theoretic risk of eliciting hypertensive or hypotensive responses with high- and low-salt diets, the research team has decades of experience giving low- and high-salt diets and have demonstrated the salt diets are well tolerated and safe. Indeed, the salt content of the “high-salt” diet is 25-55% higher than the “average” salt diet for people living in middle Tennessee. The low-salt diet is also well tolerated, with low rates (<10%) of withdrawal, which we have accounted for in our sample size and power calculations. We have not observed hypovolemia or hypotension on the low-salt diet, even in lean healthy individuals. All subjects will be monitored for adverse effects and during the study visits a physician will be available to monitor the safety of the subject through the protocol, and between study visits, a physician will be available 24 hours a day by phone and/or pager to subjects.

Private health information: This information will be collected during the course of the study. However, only key study personnel will have access to this information, which will be stored in a HIPAA compliant, password protected REDCap database. No protected health information will be shared with employers, insurers, or non-research personnel.

7.0 Reporting of Adverse Events or Unanticipated Problems Involving Risk to Participants or Others

Adverse events (AEs) will be reported according to IRB policies and procedures. Reporting will depend on adverse event severity:

Grading of Severity

0. No AE or within normal limits.
1. Mild AE.
2. Moderate AE.
3. Severe AE resulting in inpatient hospitalization, or a persistent or significant disability/incapacity.
4. Life-threatening or disabling AE.
5. Fatal AE.

AE's of grade three or higher will be reported immediately to the IRB using the Report of Adverse Events per IRB policies and procedures. Every six months the PI will summarize any AE's to the IRB. In conjunction with the IRB, the PI will determine if modifications to the protocol are warranted.

Serious and unexpected adverse events will be reported to our IRB within ten working days. All our adverse events will be reported as required at the time of continuing review. Protocol deviations and violations will be reported to our IRB within ten working days.

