2.0 Rationale and Specific Aims

The following hypotheses and specific aims were designed in response to a recent call from the American Heart Association (AHA) for i) standardized biomarkers to enable the clinical diagnosis of SSSB and ii) improved understanding of human tissue salt storage mechanisms²⁵.

Hypothesis 1: Tissue sodium content is elevated in adults predisposed for SSSB; tissue sodium and adiposity provide biomarkers for SSSB. **Aim 1:** Black adults without hypertension (20 male; 20 female) with BMI range=18 to 40 kg/m² and age range=18-55 years will be assessed for SSSB according to recent guidelines²⁶, and scanned using MRI to quantify tissue sodium and fat fraction in the lower extremities. Multivariable analyses will be applied to quantify relationships between tissue sodium, fat fraction as a surrogate of BMI, age, and sex with SSSB status. **Impact.** Unique tissue sodium and fat profiles may provide internal, mechanistic biomarkers of SSSB that could be used as endpoints in clinical trials of SSSB.

Hypothesis 2: Tissue sodium content is elevated in tissues affected by impaired lymphatic flow in adults with SSSB. **Aim 2:** The same participants will be scanned using noninvasive MR lymphangiography to quantify lymphatic flow velocity in the lower extremities. Non-parametric tests will be applied to evaluate the association between lymphatic flow and tissue sodium content in adults evaluated for SSSB. **Impact.** Identifying the extent of lymphatic dysfunction in SSSB could motivate novel treatment strategies to improve lymphatic pumping and tissue sodium clearance.

Hypothesis 3: Elevated tissue sodium content is associated with reduced renal perfusion in adults with SSSB. **Aim 3:** The same participants will be imaged using noninvasive MR spin-labeling techniques to measure kidney perfusion (ml blood/100g

tissue/min). Non-parametric tests will be applied to evaluate the association between kidney perfusion and peripheral tissue sodium content in adults evaluated for SSBP. Impact. Imaging of renal cortical circulation, where sodium-filtering nephrons are located, related to tissue sodium stores in SSBP may have potential to portend salt sensitive hypertension.

The overall goal of this work is to provide noninvasive imaging tools to assess a more complete spectrum of mechanisms underlying SSBP, which will motivate the use of these tools in future clinical trials to evaluate risk of SSBP or therapies to modify tissue sodium storage.

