4.0 Enrollment/Randomization

We will enroll 20 black adults (10 female and 10 male) who meet the inclusion and exclusion criteria. To analyze study hypotheses, and for comparison to normal weight individuals, we will share data from the study cohort of [name] (IRB #151943).

The following recruitment approaches will be used: Vanderbilt CTSA (VICTR) Research Notification Distribution List, the linked email system which reaches Vanderbilt faculty and staff, as well as members of the Middle Tennessee community, and ResearchMatch, a national online registry maintained at Vanderbilt which allows people to self-register and express interest as research participants. Additional patients may be recruited from external sites. IRB approved flyers/advertisements of the study may be distributed in the public local to Vanderbilt and surrounding areas as additional means of subject recruitment for this study. The SUBJECT LOCATOR program is part of a toolset available through VICTR that enables teams to specify inclusion/exclusion criteria for a specific study. The inclusion/exclusion criteria are codified for computable use and combined with data coming through VU Clinical Systems to proactively identify individuals who might qualify for a study. Once a 'match' is made, research study personnel are alerted using confidential messaging or a secure web portal and they may then use the information to further review the subject's information using the Vanderbilt Electronic Medical Record. If the subject is further deemed a candidate for the study, the study personnel will notify the subject's care provider who will then ask the subject if they would be interested in communicating with study personnel.

At the screening visit, history study consent will be obtained, a medical and physical examination administered, and protocol eligibility determined. If a subject meets inclusion criteria, without any exclusion criteria, the subject will be enrolled. Subjects will receive serial low- and high-salt diets in a randomized crossover design. The randomization (using permuted blocks) will occur to one of two dietary sequences: (1) high-salt, washout, then low-salt diet, or (2) low-salt, washout, then high-salt diet. Randomization assignment will occur at screening and before baseline to ensure sufficient time to prepare the subjects' provided meals.

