9.0 Statistical Considerations

Subjects who are overweight or obese (n=20) will be recruited through this IRB. To analyze study hypotheses, and for comparison to normal weight individuals, we will share data from the study cohort of [name] (IRB #151943). This will include identical data acquired from at least n=20 subjects who are normal weight (18 to <25 kg/m²) and who meet identical inclusion/exclusion criteria.

Statistical analysis procedures for Aim 1: Statistical analyses will be performed by key study personnel and members of the Center for Quantitative Sciences at the VUMC. The primary statistical objective of Aim 1 is to test the hypothesis that adults who are salt sensitive have higher baseline tissue sodium relative to adults who are not salt sensitive. To test this, we will divide participants into those who are salt sensitive (SS, ≥5 mmHg change in mean arterial pressure ΔMAP following high salt diet compared to low salt diet) or not salt sensitive (NSS, <5 mmHg ΔMAP), according to a review of methods and recommendations from Kurtz et al.²⁶. The metric ΔMAP represents a continuous variable of SSBP. A Mann Whitney U test will be applied to determine whether tissue sodium content is significantly different in SS and NSS groups. Based on a prior study of tissue sodium storage in adults who are hypertensive (n=10)

or normotensive (n=12)¹⁹ we anticipate a similar difference in tissue sodium of 6±4 (mean ± standard deviation, mmol/L) between SS and NSS adults. Our study is designed to provide at least 80% power to detect differences in tissue sodium with a two-sided significance of p<0.05.

Our secondary statistical objective of Aim 1 is to test the hypothesis that tissue sodium content and potential risk factors for SSBP, including biological sex, age, and tissue fat/water fraction as a sensitive surrogate of BMI, are related to Δ MAP as a continuous variable. We will apply multivariable regression analysis using tissue sodium, fat/water fraction, biological sex, and age as independent variables, and Δ MAP as the dependent variable among all participants. With a sample size of 40 , we should be able to evaluate the four predictors of Δ MAP (each with one degree of freedom) without over-fitting the model.

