(see mentor support letter). The primary statistical objective of Aim 1 is to test the hypothesis that adults who are salt sensitive have elevated baseline tissue sodium relative to adults who are not salt sensitive. To test this, we will apply a previously-published, informed cutoff to dichotomize participants into those that are salt sensitive (SS, ≥ 5 mmHg reduction in Δ BP depletion) or salt resistant (SR, < 5 mmHg reduction in Δ BP), according to a review of methods and recommendations from Kurtz *et al.*¹¹. The metric Δ BP represents a continuous variable of SSBP; tests for normality and homoscedasticity will be made. Depending on normality, a Mann Whitney U test or a Student's t-test will be applied to determine whether muscle sodium content is significantly different in SS and SR groups, matched for race and accounting for biological sex as a covariate. Based on a prior study of tissue sodium storage in adults with hypertension (n=10) and normotensive (n=12)²⁶ we anticipate a similar difference in tissue sodium of 6 ± 4 (mmol/L) between SS and SR adults. With a sample size of 20 in each group, our study design will provide at least 80% power to detect differences in tissue sodium with a two-sided significance of $p<0.05$.

Our secondary statistical objective of Aim 1 is to test the hypothesis that muscle sodium content and potential risk factors for SSBP, including biological sex and tissue fat/water fraction as a sensitive surrogate of BMI, are related to Δ BP as a continuous variable. We will apply multivariate regression analysis using muscle sodium, fat/water fraction, and biological sex as independent variables, and Δ BP as the dependent variable among all participants. With a sample size of 40, we will have sufficient power to evaluate three predictors of Δ BP at the

Statistical analysis procedures for Aim 2:

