Statistical analysis procedures for Aim 3: The primary statistical objective of Aim 3 is to test the hypothesis that elevated tissue sodium content is associated with reduced renal perfusion in adults with SSBP. To test this hypothesis, we will calculate either the Pearson's- r or Spearman's-rho correlation coefficient, depending on normality, between renal cortical perfusion and peripheral tissue sodium content in adults who are SS or SR and matched for age, race, and BMI, and accounting for biological sex as a covariate. The correlation coefficient and adjusted p-values and 95% confidence intervals will be reported for each test. Based on our preliminary data in normotensive black women who display a Spearman's-rho=0.49 between tissue sodium and fat/water fraction (**Table 1**), we anticipate a similar or greater correlation with renal perfusion; with 20 subjects in each group, our design will provide 80% power to detect a correlation with two-sided significance of $p<0.05$ between tissue sodium content and renal cortical perfusion. Next, to compare the relationships in the SS group between i) tissue sodium and lymph flow velocity and ii) tissue sodium and renal cortical perfusion, a linear regression for each relationship with robust errors and an interaction term will be applied. The covariates will be biological sex and fat/water fraction. The coefficient for the interaction will be quantified as the difference between the slopes.

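### The protocol says withdrawal is allowed for in the sample size, but no calculation shows an adjustment, and the Aim 1 test, Aim 1 regression and Aim 3 assume that nobody withdraws

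*Protocol*

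**What the plan says.** In the paragraph on tolerability of the diets, Protocol section 6.0 reports "low rates (<10%) of withdrawal, which we have accounted for in our sample size and power calculations". The planned numbers are these:

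- **Enrolment (Protocol 4.0):** "We will enroll 20 black adults (10 female and 10 male) who meet the inclusion and exclusion criteria".
- **Shared cohort (Protocol 9.0):** "This will include identical data acquired from at least n=20 subjects who are normal weight". With the 20 enrolled, this gives the 40 participants named under Aim 1 in Protocol 2.0.
- **Aim 1 comparison:** Protocol 9.0 claims at least 80% power without giving a group size. SAP 6.1 makes the same claim for 20 per group.
- **Aim 1 regression:** Protocol 9.0 uses 40 participants and four predictors. The SAP has three predictors: "With a sample size of 40, we will have sufficient power". That SAP sentence breaks off in the available text, so only its sample size is relied on here.
- **Aim 2 (SAP 6.1):** 16 per group, 80% power.
- **Aim 3 (SAP 6.1):** "with 20 subjects in each group, our design will provide 80% power to detect a correlation", assuming a correlation of 0.49 or greater.

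**The concern.** A reader of section 6.0 will take 20 per group and 40 in total as numbers left after withdrawal. They are the planned numbers before it.

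The loss matters because the salt-sensitivity measure is the difference in blood pressure between the two diets. A participant who leaves before the second diet visit has no value for it. That person cannot be classified as salt sensitive or not, and drops out of the group comparison and the regression. SAP section 10 also limits the primary outcome to randomised participants who went through the diets without major deviations. Protocol section 8.0 lists other ways to leave the study, including noncompliance, pregnancy and loss to follow-up, whereas the quoted rate is given for the low-salt diet.

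At stake are the accuracy of an assurance about the design, the Aim 3 power statement and the number on which the regression claim rests.

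**Working it through.** **Inputs.** Withdrawal is taken as 10%, the upper bound in Protocol 6.0. For Aim 1, Protocol 9.0 gives "similar difference in tissue sodium of 6±4 (mean ± standard deviation, mmol/L) between SS and NSS adults", so the standardised difference is d = 6/4 = 1.5. For Aims 2 and 3 the correlation is 0.49 (SAP 6.1). Alpha is 0.05, two-sided. Equal groups are the SAP's assumption; the actual split is known only after the diets.

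**1. Is there an inflation step?** The planned total is 20 + 20 = 40. The Aim 1 comparison uses 20 + 20 = 40, the regression uses 40 and Aim 3 uses 20 + 20 = 40. Nothing is held back in any of these. To end with 20 completers after 10% loss, 20/0.9 = 22.2, so 23 would have to start. Aim 2 uses 16 + 16 = 32; since 16/0.9 = 17.8, 18 starters per group would suffice there.

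**2. Evaluable numbers at 10% loss.**
- If only those enrolled here withdraw: 20 × 0.9 = 18, and 18 + 20 = 38.
- If the shared cohort is assumed to lose 10% too: 40 × 0.9 = 36, or 18 per nominal group.

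**3. Aim 1 comparison.** Normal approximation: power = Φ(d√(n/2) − 1.96).
- n = 20 per group: 1.5 × √10 = 4.743; Φ(2.783) = 99.7%. The plan's claim of at least 80% is reproduced.
- n = 18 per group: 1.5 × √9 = 4.5; Φ(2.54) = 99.4%.

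The noncentral t gives 99.6% and 99.2%. A 5,000-run Mann-Whitney simulation with normal data gives 99.5% and 98.9%. With an uneven split of 30:10 (an assumption, near the 74% prevalence in Protocol 1.0), the noncentral t gives 97.9%, and 96.6% at 27:9 after 10% loss. The minimum for 80% is 7 per group by the normal approximation and 9 by the noncentral t.

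**4. Aim 3 correlation within a group.** Fisher z: power = Φ(atanh(0.49) × √(n − 3) − 1.96), with atanh(0.49) = 0.536.

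| n per group | 0.536 × √(n − 3) | minus 1.96 | Power |
|---|---|---|---|
| 20 (stated as 80%) | 2.210 | 0.250 | 60% |
| 19 (38 split evenly) | 2.144 | 0.184 | 57% |
| 18 | 2.076 | 0.116 | 55% |

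The stated 80% is not reproduced even with no withdrawal. Using a Spearman variance of 1.06/(n − 3), the figures are 57% at n = 20 and 52% at n = 18. The gap from 80% to 55% is 25 points: about 20 exist before anyone withdraws, and about 5 come from the loss. For 80% power, n = ((1.96 + 0.842)/0.536)² + 3 = 30.3, so 31 per group.

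**5. Aim 1 regression.** Participants per predictor is a yardstick used here; the documents state no such ratio. With the protocol's four predictors: 40/4 = 10, 38/4 = 9.5, 36/4 = 9. With the SAP's three: 40/3 = 13.3, 38/3 = 12.7, 36/3 = 12.

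**The case against.** The best defence is that withdrawal can be absorbed by spare power as well as by enrolling more people. The protocol's only power statement is the one for Aim 1, which promises at least 80%. Under 6±4 that needs 7 to 9 per group, so 10% withdrawal leaves it intact. This stands for Aim 1. However, neither document says that the headroom was meant to cover withdrawal, and it does not extend to Aim 3 or to the regression statement.

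Three stronger readings are tempting, and the documents do not support them.

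- **A reader might infer that every calculation uses the full planned number.** Aim 2 uses 16 per group, which could absorb up to 20% loss from 20 (4/20). Nor can Aim 2 be credited as the allowance: the SAP gives no such reason, 16 of 20 does not correspond to a rate below 10%, and Aim 3 uses 20 with the same correlation, power and alpha.
- **A reader might infer that the study has no capacity to bear withdrawal.** Aim 1 clearly has it. The shared cohort is also a minimum and not a fixed 20, so extra shared participants could offset some loss. They would be of normal weight, though, and could not stand in for the overweight and obese participants enrolled here.
- **A reader might infer that withdrawal takes Aim 3 from 80% to 55%.** Most of that gap is a separate fault in the stated power. If the two groups were pooled, Fisher z power would be 90% at n = 40 and 87% at n = 36, but the SAP states its figure for 20 in each group.

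It is also fair to say that the 36-completer case is an assumption, because the shared data are described as already acquired. The documents do not say whether withdrawn participants are replaced; replacement would restore the 20.

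**Conclusion.** The statement in Protocol 6.0 is not supported by any calculation in the protocol or the SAP. The Aim 1 comparison, the Aim 1 regression and Aim 3 are worked as if all planned participants complete. That much follows from the text alone.

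The consequence is modest. Power for the Aim 1 primary comparison stays at about 99% with 18 per group. Aim 3 falls from about 60% to about 55%, against a stated 80% that the design does not deliver even without withdrawal. The regression rests on 36 to 38 participants, not 40.

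These sizes assume a 10% loss, no replacement, equal salt-sensitive and non-sensitive groups, the plan's own effect sizes, and Aim 3 power computed within each group.

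**What to change.** Either delete the claim in Protocol 6.0 that withdrawal was allowed for, or make it true on paper:

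- State the expected evaluable number: 38 if 10% of the 20 enrolled here withdraw, or 36 (18 per nominal group) if the shared cohort is assumed to lose 10% as well. State which assumption is used and whether withdrawn participants are replaced.
- Restate the Aim 3 power in SAP 6.1 for that number: about 55% at 18 per group for a correlation of 0.49.
- Base the Aim 1 regression statements in Protocol 9.0 and SAP 6.1 on 36 to 38 participants in place of 40.
- Say that Aim 1 keeps its 80% through headroom under the 6±4 assumption, not through an inflation for withdrawal.
- Give the reason for 16 per group in Aim 2, whether or not it relates to withdrawal.

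The cost is wording. Enrolment and procedures do not change, but the Aim 3 power statement becomes less favourable, mostly for reasons other than withdrawal.
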